5.0 Treatment Protocol

- 5.1 This will be a four-arm clinical trial of an intervention examining the feasibility and efficacy of calcitriol 45 µg alone, a structured home-based walking/progressive resistance exercise program alone, along with the combination of calcitriol 45 µg and a structured home-based walking/progressive resistance exercise program for the maintenance of proper bone health among invasive breast cancer survivors.
- 5.2 Potentially eligible subjects at Strong Memorial Hospital will be approached by their physician either at a regularly scheduled oncology appointment or by standardized letter in the mail. The initial contact will assess whether the patient has any interest in participating in a clinical trial to preserve bone health. If interested, patients will be invited to call or come to our research center for screening to determine their eligibility for the study. If the patient is eligible, study personnel will explain the details of the study and obtain informed consent from patients who agree to participate.

5.3 Consent Process and Initial Assessments

- 5.3.1 Cancer survivors less than 5 years removed from the diagnosis of breast cancer who meet the eligibility criteria including approval from their physician will be invited to participate in the trial.

Upon consent, with help from the study coordinator, the patient will complete an On-Study Data Form, a Clinical Record Form, and a Medication Form, providing clinical and demographic data. Questions concerning the patient's sun exposure history, medical history, supplement usage history, exercise history, and baseline brief symptom inventory are also included. The study coordinator will obtain information necessary to complete these three forms from the patient's medical records when the patient is unable to provide this information in sufficient detail (e.g., staging, Karnofsky Performance Scale, surgical procedures, types and doses of treatments). Additionally, patients will be evaluated on vitals (Resting Heart Rate, Height, Weight & Blood Pressure), aerobic capacity (VO₂max Treadmill Test and Resting Metabolic Rate (RMR) test) muscular strength (Handgrip Dynamometry and 7-10 repetition maximum test), skeletal muscle mass (Bioelectrical Impedance Analysis), and physical activity. (Note: Baseline measures of physical activity involve fitting each participant with a Pedometer for a 5-day baseline assessment). Patients will also provide a blood sample at this time.

- 5.3.2 Patients will be randomized to one of four treatment arms. Study medication and instructions for calcitriol 45 µg will be given and reviewed with all patients. Arm 2 and arm 3 patients will also receive instructions and an Exercise Kit for the home-based walking and progressive

resistance exercise program.

5.3.2.1 Patients assigned to Treatment Arm 1 will receive a 12-week supply of calcitriol, which consists of twelve 45 μ g pills of calcitriol to be taken once a week (QW).

5.3.2.2 Patients assigned to Treatment Arm 2 will receive a 12-week supply of daily multivitamins and a home-based walking and progressive resistance exercise regimen to follow for a total duration of 12 weeks.

5.3.2.3 Patients assigned to Treatment Arm 3 will receive a 12-week supply of calcitriol, which consists of twelve 45 μ g pills of calcitriol to be taken once a week (QW) and a home-based walking and progressive resistance exercise regimen to follow for a total duration of 12 weeks.

5.3.2.4 Patients assigned to Treatment Arm 4 will receive a 12-week supply of daily multivitamins but will not receive an exercise regimen to follow during the study period.

5.4 Physiological and Psychological Assessments

- 5.4.1 Blood sampling at four time points (baseline, day 5, week 6, and week 12) will be done to estimate bone resorption and formation and as a safety check for hypercalcemia. Measures of bone pathology will be performed through the Associated Regional and University Pathologists (ARUP) Laboratories. Pre and post-intervention tests for Cross-linked N-teleopeptide of type I collagen (NTx), a specific indicator of bone resorption will be performed. In addition, pre and post-intervention tests for bone-specific alkaline phosphatase (BAP), an indication of bone formation, will be performed.
- 5.4.2 The blood draws for estimation of NTx and BAP will use 2 red top tubes for serum.
- 5.4.3 All blood draws will occur in the General Clinical Research Center (GCRC) and the blood will be drawn by research personnel in the GCRC. The time of day will be noted, with future assessments at approximately the same time of day during post-testing and follow-up.
- 5.4.4 All patients will be given a measure of physical activity (Aerobics Center Longitudinal Physical Activity Questionnaire (ACLS)), fatigue

(Functional Assessment of Chronic Illness Therapy Fatigue Subscale (FACIT-F); Brief Fatigue Inventory (BFI); Multidimensional Fatigue Symptom Inventory (MFSI)), QOL (Functional Assessment of Chronic Illness Therapy with Fatigue (FACIT-F)), to complete at home at the appropriate times (i.e. during baseline and post-testing). (Note: Pilot use of the questionnaire packet indicates an average completion time of ≤ 30 minutes).

[figure not shown]
5.4.5 All patients will be evaluated on aerobic capacity (VO₂max Treadmill Test), muscular strength (handgrip dynamometry, 7-10 repetition maximum test), gait (tandem walk test), and skeletal muscle mass (bioelectrical impedance). All physiological fitness testing will be administered according to the Guidelines for Exercise Testing and Prescription (GETP) as outlined by the American College of Sports Medicine (ACSM).

5.5 Calcitriol 45 μ g Arms 1 & 3

5.5.1 The calcitriol 45 μ g arms 1 & 3 will follow the guidelines listed below:

5.5.1.1 The calcitriol 45 μ g pills will be supplied by Roswell Park Cancer Institute and the State University of New York at Buffalo. The pills will be placed in a tamper-proof blister pack. Research subjects will be instructed to take the calcitriol on an empty stomach, 1 to 2 hours prior to or after any meal. Subjects will also be advised to increase their intake of water by 4 cups on the day of taking the pill and the day after. Subjects will take 1 capsule 1 day a week for a duration of 12 weeks. Subjects will be supplied with the full 12 weeks of capsules that will be dispensed by the University of Rochester Medical Center pharmacy.

5.5.1.2

5.5.1.3 The study coordinator will contact each subject on the day she is scheduled to take calcitriol 45 µg as a reminder. The study coordinator will use this opportunity to assess any potential complications or toxicities due to the intervention.

5.5.1.4 Because of improved calcium absorption from the gastrointestinal tract caused by calcitriol, most participants may be maintained on a lower calcium intake. Most patients on calcitriol require only dietary sources of calcium and need no supplementation. Therefore, participants must not take multivitamin or calcium supplementation while on the study medication. In addition, ingestion of large amounts of foods containing dairy products should be avoided. Participants assigned to calcitriol who are routinely taking a multivitamin supplement may continue the supplement as long as the amount of vitamin D in the supplement is not in excess of the RDA (recommended daily allowance) of 400 IU or 10 µg. If they are not taking a multivitamin supplement, they will be asked to not start supplementation while on study.

5.5.2 Toxicity Monitoring:

After the first dose of calcitriol is administered on day 0, the patients will return for blood collection on day 5. On day 5, any patient displaying any grade ≥ 3 toxicity related to the study drug will be removed from the study. The patients will return at 6 weeks and 12 weeks for blood collection. These visits will be coordinated with surgical oncology visits, medical oncology visits, or radiation oncology visits, when possible, to reduce patient burden. Following her appointment, the patient will proceed directly to phlebotomy.

Removal from study: Patients will be removed from the study for any of the following reasons:

1. Any grade ≥ 3 toxicity related to the study drug.
2. A grade 2 toxicity that persists for more than 2 weeks.
3. Withdrawal of consent.

For any clinically adverse event, the toxicity grading scale established by the FDA will be used. It is as follows:

Grade 1 toxicity (Mild): No interference with activity

Grade 2 toxicity (Moderate): Some interference with activity not requiring medical intervention.

Grade 3 toxicity (Severe): Prevents daily activity and requires medical intervention.

Grade 4 toxicity (Potentially Life Threatening): ER visit or hospitalization.

For hypercalcemia, the FDA toxicity grading scale specific to serum calcium will be used:

Grade 1 toxicity (Mild): 10.3-11.0 mg/dL

Grade 2 toxicity (Moderate): 11.1-11.5 mg/dL

Grade 3 toxicity (Severe): 11.6-12.0 mg/dL

Grade 4 toxicity (Potentially Life Threatening): > 12.0 mg/dL

The FDA toxicity grading scale will be used for determining all adverse events.

In addition to blood safety checks throughout the study, a research coordinator will call each patient at on the day of the week she is scheduled to take calcitriol 45 µg to ensure compliance and assess side effects. The nurse will record any adverse events (AE) and/or serious adverse events (SAE). Any patient who reports an AE or SAE will be scheduled for a clinical visit. In addition, the research coordinator will inquire as to any change in over the counter supplement usage. Reports regarding potential toxicities, patient safety, and outcomes will be submitted to the University of Rochester Medical Center Research Subjects Review Board (RSRB). The potential risks and side effects of calcitriol include:¹⁵⁵

Because calcitriol is the active analog of vitamin D, adverse effects are similar to those found with excessive vitamin D intake. Because of the short biological half-life of calcitriol, elevated serum calcium levels normalize within a few days, much more quickly than with native vitamin D supplementation.

Early signs and symptoms of vitamin D intoxication: Weakness, headache, somnolence, nausea, vomiting, dry mouth, constipation, muscle pain, bone pain, metallic taste, anorexia, abdominal pain, or stomach ache.

Late signs and symptoms of vitamin D intoxication: Polyuria, polydipsia, anorexia, weight loss, nocturia, conjunctivitis, pancreatitis, photophobia, rhinorrhea, pruritus, hyperthermia, decreased libido, elevated BUN,

albuminuria, hypercholesterolemia, elevated SGOT and SGPT, ectopic calcification, nephrocalcinosis, hypertension, cardiac arrhythmias, dystrophy, sensory disturbances, dehydration, apathy, arrested growth, urinary tract infections, and, rarely, overt psychosis.

This protocol requests a Comprehensive Metabolic Profile (Panel 14) from the GCRC. Of main concern is serum calcium, specifically hypercalcemia. A serum calcium level between 8.4 and 10.2 mg/dL is considered normal. Any level > 10.2 mg/dL or < 8.4 mg/dL is considered outside the safety range and the investigators should be notified.

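### Can the removal rule for grade 2 toxicity beyond 2 weeks be applied to symptom-free hypercalcemia when the scheduled on-treatment draws are 37 and 42 days apart?

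*Combined protocol and SAP*

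**What the plan says.** The removal list in Section 5.5.2 has three grounds: any drug-related toxicity of grade 3 or higher, "A grade 2 toxicity that persists for more than 2 weeks", and withdrawal of consent. Hypercalcemia has its own scale in the same section, defined by the laboratory value only: "Grade 2 toxicity (Moderate): 11.1-11.5 mg/dL".

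Section 5.4.1 sets the schedule: "Blood sampling at four time points (baseline, day 5, week 6, and week 12) will be done", in part as a check for hypercalcemia. Section 5.5.2 repeats it for the calcitriol arms (day 5 after the first dose, then "The patients will return at 6 weeks and 12 weeks for blood collection") and adds "These visits will be coordinated with surgical oncology visits, medical oncology visits, or radiation oncology visits, when possible". The table in Section 8.0 lists toxicity monitoring at the same four times. Dosing is weekly (Section 5.5.1.1): "Subjects will take 1 capsule 1 day a week for a duration of 12 weeks".

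For a calcium above 10.2 or below 8.4 mg/dL, Section 5.5.2 says that it "is considered outside the safety range and the investigators should be notified". Section 5.5.3.1 includes abnormal laboratory findings among adverse events. Section 5.5.5 gives the investigators continuous review of safety data. Between draws there is a weekly telephone call on the dosing day (Sections 5.5.1.3 and 5.5.2), and a patient who reports an adverse event is given a clinical visit.

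**The concern.** A rule about duration needs at least two observations, spaced in a way that bears on the duration. A symptomatic toxicity can be followed through the weekly calls. A raised calcium without symptoms can be followed only by another blood test, and the visible text schedules none between day 5 and week 6, or between week 6 and week 12. It states no repeat test, no interval for one, and no meaning of persistence for a grade defined by a laboratory value.

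At stake would be the even application of a mandatory removal rule to the toxicity that Section 5.5.2 names as its main concern. Two symptom-free patients with the same day 5 value might be handled differently, while weekly doses continue to fall due.

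**Working it through.** **Inputs.** Draws on nominal days 0, 5, 6 × 7 = 42 and 12 × 7 = 84 (Sections 5.4.1, 5.5.2 and 8.0). Duration limit 2 × 7 = 14 days; grade 2 calcium 11.1 to 11.5 mg/dL; notification above 10.2 mg/dL (all Section 5.5.2). Calcitriol arms: 2 arms of 18 (Section 4.1.2). The plan states no figure of its own on this point.

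**Step 1: spacing.** On-treatment gaps are 42 − 5 = 37 days and 84 − 42 = 42 days, both longer than 14.

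**Step 2: where the limit falls.**

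| Grade 2 value first seen | Limit reached | Next scheduled draw | Draw falls after limit by |
|---|---|---|---|
| Day 5 | 5 + 14 = day 19 | Day 42 | 42 − 19 = 23 days |
| Day 42 | 42 + 14 = day 56 | Day 84 | 84 − 56 = 28 days |

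**Step 3: what scheduled draws can show.** A continuous episode shorter than 37 days cannot include two of days 5, 42 and 84. Take a patient with normal calcium at day 0, grade 2 at day 5 and a lower value at day 42. The episode began after day 0 and ended before day 42, so it lasted anywhere from under 1 day to almost 42 days, on both sides of 14. (This assumes that calcium was normal on day 0. Section 3.5 sets entry on corrected calcium and does not say how close to the first dose it is measured.) Grade 2 values at both day 5 and day 42 are compatible with persistence but do not prove it: the protocol says that "elevated serum calcium levels normalize within a few days", and with weekly dosing a recurrence would look the same.

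So the scheduled draws by themselves do not settle the duration of a symptom-free grade 2 episode.

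**Step 4: does the text limit calcium testing to those draws?** Sections 5.4.1, 5.5.2 and 8.0 list planned collections. None says that calcium is measured only then, and none bars an unscheduled test.

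**Step 5: does a flagged value reach someone who can act?** The lowest grade 2 value, 11.1 mg/dL, is 11.1 − 10.2 = 0.9 mg/dL above the notification threshold, so every grade 2 result at a scheduled draw is to be notified. It is also an adverse event by definition and falls under continuous investigator review. The investigators then hold a flagged value and a mandatory rule that turns on how long it lasts. Applying the rule implies finding that out.

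**Step 6: who is outside the question.** For grade 3 or higher, one value is enough. Symptomatic grade 2 events can be followed through the weekly calls and the visits they prompt. An episode lying wholly between two draws is never flagged; that concerns how often calcium is drawn routinely, which is a clinical choice and not a matter of how the duration rule is read.

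**Step 7: size.** The ceiling is 2 × 18 = 36 of 72 planned patients. Section 1.6 gives 54 in all, for which an equal split would make it 27. The actual number is unknown. Section 1.4 reports that adverse events were very uncommon at this dose in earlier trials.

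**The case for a change.** The best case for a change is that removal is mandatory, yet for this one kind of event it depends on a test that nobody is told to order. Notification and review do not produce a second calcium value. The clinical visit in Section 5.5.2 follows an event that the patient reports, and a symptom-free patient has nothing to report. All 12 weeks of capsules are dispensed at once, so no later dispensing step would reopen the matter. After a day 5 value, doses fall due on days 21, 28 and 35, beyond the day 19 limit and before the next scheduled draw.

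The facts in this stand: no visible passage scripts a recheck, and the weekly calls ask about side effects and do not measure calcium. The inference is weaker. The dose count describes exposure only if investigators who have been told of the value, and who are bound by the removal rule, let it rest until week 6, and no passage tells them to do so. The weekly call on each dosing day also keeps staff in contact with the patient. That two patients might be treated differently is possible, but nothing in the documents shows that it is likely. Finally, this is purely an argument from absence, and item 5.5.1.2, in the calcitriol guidelines just before the toxicity section, is blank in the public text.

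**Conclusion.** The date arithmetic is right and the conclusion drawn from it is too strong. The routine draws, 37 and 42 days apart, are there to detect a raised calcium; follow-up of a flagged value is what would establish its duration. The two can stand together, so the passages leave a detail unstated and do not conflict. Notified investigators can be expected to fill it sensibly, and how they do so is for clinical judgement.

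Nothing in the statistical plan turns on it. Section 7.0 analyses changes in NTx and BAP, and neither it nor the secondary analyses use the duration of a toxicity. The only route to the data is whether an individual patient stays on study, for a number that is unknown and at most 36.

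This rests on three assumptions: unscheduled calcium tests are available to the investigators, notification happens as written, and blank item 5.5.1.2 contains nothing that restricts follow-up. If the protocol is being edited for other reasons, a sentence on how persistence is established for a laboratory-graded event would be a courtesy to site staff; it is not a reason to amend.

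### No planned calcium falls within 2 weeks of a grade 2 value, so the 2-week removal rule cannot be applied on time to asymptomatic hypercalcemia unless the investigator chooses to retest

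*Combined protocol and SAP*

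**What the plan says.** Section 5.5.2 lists the reasons for removal. The first is a drug-related toxicity of grade 3 or higher. The second is "A grade 2 toxicity that persists for more than 2 weeks". For hypercalcemia the same section grades by serum calcium: "Grade 2 toxicity (Moderate): 11.1-11.5 mg/dL".

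Section 5.4.1 sets the draws: "Blood sampling at four time points (baseline, day 5, week 6, and week 12) will be done", partly as a check for hypercalcemia. Section 5.5.2 repeats the later visits ("The patients will return at 6 weeks and 12 weeks for blood collection"), and the section 8.0 schedule marks toxicity monitoring at the same four times.

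The stated action on the first on-treatment result is "On day 5, any patient displaying any grade ≥ 3 toxicity related to the study drug will be removed from the study". Nothing comparable is written for grade 2. For any calcium above 10.2 mg/dL, section 5.5.2 asks that the investigators be told.

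Between draws there is a weekly telephone contact (5.5.1.3: "The study coordinator will contact each subject on the day she is scheduled to take calcitriol"). Section 5.5.2 adds: "Any patient who reports an AE or SAE will be scheduled for a clinical visit". Under 5.5.1.1 there is no refill visit: "Subjects will be supplied with the full 12 weeks of capsules".

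**The concern.** A rule based on persistence over 14 days needs a measurement at about 14 days. For symptoms the weekly calls can supply it. For calcium they cannot, and the planned draws lie much further apart than 14 days. A woman with a grade 2 calcium and no symptoms could therefore continue weekly 45 µg doses past the point at which the sponsor's own rule would remove her, with no planned test to show whether the rule applies.

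This matters because section 1.2 makes safe participation in high-dose calcitriol a question for the pilot, and section 5.5.2 names hypercalcemia as its main safety concern. The rule covers both calcitriol arms, planned at 18 women each (section 4.1.2), so 36 women.

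**Working it through.** The plan gives no figure for this point; the check is calendar arithmetic.

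**Inputs**
- Doses: twelve of 45 µg, once weekly, the first on day 0 (5.3.2.1, 5.3.2.3, 5.5.1.1, 5.5.2). Dose days are 0, 7, ..., 77. The course is 12 × 45 = 540 µg.
- Draws after baseline: day 5, week 6, week 12 (5.4.1, 5.5.2). Assumption: weeks 6 and 12 are days 42 and 84.
- Limit: date of the grade 2 value + 14 days (5.5.2, second removal reason).

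**Results**

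| | Grade 2 on day 5 | Grade 2 at week 6 |
|---|---|---|
| Next planned calcium | day 42 | day 84 |
| Gap | 42 − 5 = 37 days | 84 − 42 = 42 days |
| 2-week limit | 5 + 14 = day 19 | 42 + 14 = day 56 |
| Limit to next calcium | 42 − 19 = 23 days | 84 − 56 = 28 days |
| Doses between draws | days 7, 14, 21, 28, 35 = 5 | days 49, 56, 63, 70, 77 = 5 (6 if the day-42 dose follows the draw) |
| Doses after the limit | days 21, 28, 35 = 3 | days 63, 70, 77 = 3 |
| Amount after the limit | 3 × 45 = 135 µg; 135/540 = 25% | 135 µg; 25% |

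The last dose is on day 77, so the week-12 draw comes 84 − 77 = 7 days after dosing has ended, and removal from treatment is then moot.

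**Sensitivity.** No visit window is stated, so I moved the week-6 visit by 7 days either way.
- Week-6 visit on day 35: the day-5 gap is 30 days with 4 doses between, 2 of them (days 21, 28) after the limit. A value at that visit is next checked 49 days later, with 4 doses (days 56 to 77) after its day-49 limit.
- Week-6 visit on day 49: the day-5 gap is 44 days with 6 doses between, 4 of them (days 21 to 42) after the limit. A value at that visit is next checked 35 days later, with 2 doses (days 70, 77) after its day-63 limit.

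Every gap is at least 30 days, more than twice the 14-day limit.

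**Grade 2 on both day 5 and day 42.** The rule could then be invoked at week 6, 23 days late. Even so, with weekly redosing and the protocol's statement that raised calcium settles within days, two values 37 days apart cannot separate one continuous episode from repeated rises after each dose.

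**The case against.** **Text that cannot be seen.** Item 5.5.1.2 is numbered but blank, and sits between the supply item and the dosing-day call. Section 5.5.5 lists dose adjustments among the items under review, yet no adjustment rule is visible. A hold-and-retest rule may exist there. This stands: the point can be made only about the visible text.

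**Investigator action.** Every grade 2 value exceeds 10.2 mg/dL, so the investigators should hear of it, and section 5.5.5 requires continuous review. Planned draws are a minimum, and nothing forbids another. A rule about persistence arguably implies that someone checks persistence. This stands in part: retesting is permitted, but the visible text neither requires it nor says when.

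**The extra clinic visit.** Section 5.5.3.1 counts an abnormal laboratory finding as an adverse event, so a grade 2 calcium could be read as prompting a visit. But the visit is tied to a patient who reports an event, which a woman without symptoms has no reason to do, and no calcium test is specified for it.

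**Low expected frequency.** Section 1.4 describes this dose as well tolerated with very few adverse events. Section 3.0 requires normal calcium at entry and excludes prior hypercalcemia and reduced renal function. Section 5.5.2 says raised calcium falls back quickly. These points limit the likely number affected. They bear less on a woman already found at grade 2: the day-5 draw comes 5 days after a dose, so a high value there has arguably already outlasted the expected fall.

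**Readings that go too far.** A reader might infer that the rule cannot work at all, or that women will be left at unsafe levels. The documents do not support either. The rule works for symptoms through the weekly calls, the first removal reason acts on a drug-related grade 3 or higher value at any draw, and a notified investigator may retest. Nor does the gap show that the sponsor's 2-week tolerance is wrong or that removal should come sooner. It shows only that the tolerance lacks a scheduled measurement.

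**Conclusion.** The gap is real and worth closing. On the planned draws, the visible text provides no calcium within 2 weeks of a grade 2 value, so in a woman without symptoms the second removal reason can be applied on time only if the investigator decides to retest. In each of the two intervals, 3 doses (135 µg, a quarter of the course) are scheduled between the limit and the next planned calcium.

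These are scheduled doses in a conditional case, not an estimate of harm: the documents give no rate of grade 2 hypercalcemia. The counts assume visits on days 42 and 84; moving the week-6 visit by a week changes 3 doses to between 2 and 4 and leaves the conclusion intact. Confidence is moderate, because item 5.5.1.2 may already hold the missing instruction.

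**What to change.** First check item 5.5.1.2 in the full protocol. If it does not cover this, add to section 5.5.2:

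> For any grade 2 serum calcium, hold the next calcitriol dose and repeat calcium within about 1 week. If the repeat is below grade 2, dosing may resume at the investigator's discretion. If it is still grade 2, keep holding and repeat just after 2 weeks from the first value; remove the patient under the second removal reason if grade 2 persists.

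For a day-5 value, the second repeat falls at about day 20, before the day-21 dose. For a week-6 value it falls at about day 57, before the day-63 dose. The hold can be given in the existing dosing-day call. The 2-week threshold is unchanged, and symptom toxicities can still be followed by the calls.

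The cost is one paragraph and, only in women with a grade 2 value, one or two extra draws and possibly one or two held doses (a third if a week-6 result is back before the day-42 dose is taken: days 42, 49 and 56). Women without a grade 2 value have no extra visit or draw.
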